7.2.3. Intensity of Adverse Event

The intensity of adverse events should be classified and recorded according to the Common Terminology Criteria for Adverse Events (CTCAE) version 4.1 in the CRF.

7.2.4. Causal Relationship of Adverse Event

Study Number: MCC 19178 IND#: Exempt

 Medical judgment should be used to determine the relationship, considering all relevant factors, including pattern of reaction, temporal relationship, de-challenge or re-challenge, confounding factors such as concomitant medication, concomitant diseases and relevant history. Assessment of causal relationship should be recorded in the CRFs.

Yes: There is a reasonable causal relationship between the investigational product administered and the AE.

No: There is no reasonable causal relationship between the investigational product administered and the AE.

- Worsening of the underlying disease or of other pre-existing conditions will be recorded as an (S)AE in the CRF.
- Changes in vital signs, ECG, physical examination, and laboratory test results will be recorded as an (S)AE in the CRF, if they are judged clinically relevant by the investigator.

7.2.5. Adverse Event and Serious Adverse Event Reporting

- Upon inclusion into the study, the patient's condition is assessed (e.g., documentation of history/concomitant diagnoses and diseases) and relevant changes from baseline are noted subsequently.
- All adverse events, serious and non-serious, occurring during the screening period or after lead-in cetuximab monotherapy (Day -14 to Day -1 of Cycle 1) prior to the first dose of the cetuximab and nivolumab combination do not need to be reported.
- All adverse events, serious and non-serious, occurring during the course of the combination of cetuximab and nivolumab treatment (i.e., from Cycle 1 Day 1 onward through the 100-day follow-up period) will be collected, documented, and reported to the sponsor by the investigator on the appropriate CRFs/SAE reporting forms.
- All adverse events will be followed for a minimum of 100 days after protocol treatment, except in cases where a study participant has started a new antineoplastic therapy. However, any SAE occurring after the start of a new treatment that is suspected to be related to study treatment by the investigator will be reported. To allow for this collection, the first Q3 month follow-up visit after the End of Treatment visit should be an in-clinic visit if possible for the patient to come to the clinic.
- Reporting will be done according to the specific definitions and instructions detailed in the "Adverse Event Reporting" section of the Investigator Site File.

 For each adverse event, the investigator will provide the onset date, end date, grade according to CTCAE v4.1, treatment required, outcome, seriousness, and action taken with the investigational drug. The investigator will determine the relationship of the investigational drug to all AEs as defined in Section 7.2.1.

IND#: Exempt

- Adverse events with onset within first administration of cetuximab therapy and 100 days after last administration of cetuximab will be considered as on treatment. All AEs, including those persisting after end of study treatment must be followed up until they have resolved or have been sufficiently characterized or the principal investigator decides to not further pursue them.
- Serious and non-serious adverse events occurring later than 100 days after last administration of trial drugs will only be reported in case they are considered drugrelated or trial (procedure) related.
- Deaths (unless they are considered drug-related or trial related) will not be reported as SAE when they occur later than 100 days after last administration of the trial.
- Although adverse events attributed to the underlying malignancy under study will be captured, disease progression itself will not be reported as an adverse event.

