Test	Pre-therapy (Day -42 to -15)	Lead-in period, cetuximab only (Day -14 before Cycle 1 only)	Every 2 weeks while on study drugs	End of Treatment (30 days after final dose) ^a	Every 3 months after EOT ^a	End of Study (2 years after EOT) ^b
Window	N/A	N/A	±3 days	±3 days	±2 week	±2 week
History and physical ^c	Χ	X	X	X	X	X
Medical History d	Х					
CBC and diff e	Χ	Х	X	X		Х
Serum chemistries f	Χ	X	X	X		X
Liver function panel ^g	X		X	X	X	X
PT, PTT, INR	Χ			X		
TSH	X		Χı	X	X	Х
Tissue for research purposes (paraffin embedded) h	Х		X (Day 8 to 14 before C1D15 treatment)	Х		
Blood for research purposes	Χ		Xm	Χ		X
Toxicity assessment i	Х	Х	Х	Х		Х
Tumor measurements ^j	Х		Χn	Xº		
Serum B-HCG k	Χ				_	
Survival Follow-up				X	X	Х

^{a.} If a subject is to start a new anticancer treatment prior to 30 days after the last study treatment it is permissible to complete this visit earlier in order to perform this safety check prior to the subject initiating subsequent treatment and thereby completing the AE follow-up period.

b. The first follow-up visit should be an in-clinic visit to complete the AE follow-up requirements listed in section 7.2.5. After this visit, once the patient is off treatment and has fully recovered from study drug-related toxicities or the patient enrolls in a hospice, the follow-up visits can be done by a phone call, in which case all procedures except survival follow-up may be omitted. If AE review is complete at first the first follow-up visit (e.g. subject started subsequent anticancer therapy) but SAE review is still required the visit can be limited to this review and conducted by a phone call or e-visit only.

c. History and physical to include ECOG performance status assessment and weight. History and physical requirement for Day 15 of each cycle is only during the phase I portion of the study. History and physical is required on only Day 1 of each cycle during the phase II portion of the study. Once the phase I portion of the study is completed (the recommended phase II dose is confirmed and approved through Moffitt's Protocol Monitoring Committee), patients enrolled at the recommended phase II dose under the phase I portion may cross over to the phase II schedule. Physical exam needs not be repeated if performed within 72 hours prior to dosing.

Study Number: MCC 19178

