- ^{d.} Relevant medical history must include smoking status (current smoker, former smoker, never smoker), number of pack years, and year of smoking cessation. Relevant medical history will also include p16 status, if known. Historic radiologic assessments will also be accessed, in accordance with protocol section 6.2, to further characterize the disease under study and to contribute to exploratory objectives.
- ^{e.} CBC and diff (complete blood count and differential) include white blood cell count, absolute neutrophil count, hematocrit, hemoglobin, platelets, % lymphocytes, % monocytes, % neutrophils, other differentials. Safety labs may be collected up to 72 hours prior to dosing.
- f. Serum chemistries include a Complete Metabolic Panel (including Na, Cl, CO2, K, BUN, creatinine, Ca) AND Mg, Phos. Safety labs may be collected up to 72 hours prior to dosing.
- ^{g.} Liver function panel includes Alk Phos, total bilirubin, SGOT (AST), SGPT (ALT), total protein. Safety labs may be collected up to 72 hours prior to dosing.
- h. If tumor paraffin blocks (or sufficient slides) are not available, fresh biopsy will be obtained before the first treatment. If fresh biopsy is indicated, one core (or punch) will be collected in formalin and the second core (or punch) will be collected in liquid nitrogen. The end of treatment optional biopsy may be performed up to 30 days after the EOT visit as scheduling may require.
- ^{i.} Toxicity assessment: Common Terminology Criteria for Adverse Events (CTCAE) version 4.1 will be used. All toxicity grades (including grade 1) should be captured on the case report forms. All toxicities that occurred during treatment and until 30 days following completion of therapy should be followed until resolution.
- ¹ Tumor measurement: The same type of scan should be used for repeat measurements. The scans may be performed up to 7 days before the projected corresponding treatment visit. Scans in screening will include: CT- or MRI-neck, CT-chest, CT-abdomen, and CT-pelvis. Response scans can be limited to the anatomy of areas of known and suspected disease. Scans must be performed with contrast.

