4.4.2. Dose Modifications for Cetuximab-related Non-Immunological Toxicities

If the patient experiences any drug-related event \leq Grade 2, the dose of cetuximab and nivolumab should be continued at the given dose level.

If the patient experiences any drug-related event ≥ Grade 3, the dose of cetuximab and nivolumab should be discontinued until resolution (to baseline) of the toxicities, or until stabilization. Upon resumption, the physician may choose to reduce the dose of Cetuximab per the table below. As an exception, continued treatment in the face of Grade 3 hypomagnesemia and hypophosphatemia will be allowed at the treating physician's discretion. Low magnesium is expected while treating with cetuximab and can be safely replenished as needed throughout treatment according to local guidelines.

If the patient experiences any acute onset or worsening pulmonary symptoms, the doses of cetuximab and nivolumab should be delayed. The management should follow the pulmonary toxicity management as detailed in Section 4.5 Table 2 Pneumonitis and Appendix 4 Pulmonary Adverse Event Management Algorithm because interstitial lung disease from cetuximab and pneumonitis from nivolumab cannot be reliably distinguished.

IND#: Exempt

In the event of Grade ≥ 3 rash, treatment with cetuximab should be paused until recovery to Grade ≤ 2 . Treatment should be resumed at a reduced dose (see Section 4.3). If Grade ≥ 3 rash does not resolve to Grade ≤ 2 within 14 days of stopping cetuximab treatment and despite optimal supportive care, the patient should not receive any further treatment with cetuximab.

In the event of a prolonged (≥7 consecutive days) Grade 2 drug-related toxicities, the investigator may choose to pause cetuximab and nivolumab for up to 4 weeks to allow the patient to recover followed by a dose reduction (the hold and reduction are both at the treating physcian's discretion). Only the cetuximab may be dose reduced, and dose reductions are according to the following table:

	Cetuximab	Nivolumab
	Cycles 1-24 (Q 2 weeks)	Cycles 1-24 (Q 2 weeks)
Dose Level 1	500 mg/m ²	240 mg
Dose Level -1	250 mg/m ²	240 mg
Dose Level -2	125 mg/m ²	240 mg

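### The on-treatment adverse event window in section 7.2.5 is set by cetuximab dates alone, and the calendar's 30-day footnote and toxicity row do not match the 100-day follow-up

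*Combined protocol and SAP*

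**What the plan says.** Section 7.2.5 sets several adverse event windows, and they do not all run from the same dates.

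- Classification: "Adverse events with onset within first administration of cetuximab therapy and 100 days after last administration of cetuximab will be considered as on treatment". Nivolumab is not named.
- Collection starts with the combination; the sentence reads in part "i.e., from Cycle 1 Day 1 onward through the 100-day follow-up period) will be collected".
- Follow-up: "All adverse events will be followed for a minimum of 100 days after protocol treatment", with an exception once a new antineoplastic therapy has started.
- Late events: "Serious and non-serious adverse events occurring later than 100 days after last administration of trial drugs will only be reported in case" they are judged related to the drugs or to trial procedures.

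The section also says that events during screening, or between the lead-in cetuximab dose and the first combination dose, need not be reported.

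The treatment study calendar adds two instructions. Footnote i says: "All toxicities that occurred during treatment and until 30 days following completion of therapy should be followed until resolution". Footnote b says: "The first follow-up visit should be an in-clinic visit to complete the AE follow-up requirements listed in section 7.2.5". The toxicity row is marked at screening, lead-in, the two-weekly treatment visits, End of Treatment and End of Study. It shows no mark in the 3-monthly column.

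On stopping, sections 4.4.2 and 5.1.5.2 say of a grade 3 or higher rash that has not settled to grade 2 or less within 14 days that "the patient should not receive any further treatment with cetuximab". Section 4.4.3 ends cetuximab after a second hypersensitivity reaction at the slower infusion rate. None of these places says what happens to nivolumab. Sections 4.4 and 4.5 require the two drugs to be held and restarted together when they are held for toxicity.

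**The concern.** This is a two-drug regimen, and toxicity of the combination is a secondary objective (section 2.2.3). A window that follows one drug works only while both drugs share a last dose date. The joint-hold rule covers interruptions and restarts; it does not address permanent stopping of one drug. If a patient stays on nivolumab after cetuximab ends, the written rule eventually labels events as off treatment while nivolumab is still being infused.

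The calendar raises a second, separate issue that does not depend on which drug stops first. Sites tend to work from the calendar. It gives 30 days where section 7.2.5 gives 100, and it does not prompt a toxicity assessment at the visit that footnote b and section 7.2.5 set aside for adverse event review. At stake are the consistency of the safety classification and the completeness of solicitation in days 31 to 100. The primary endpoint and the sample size are not involved.

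**Working it through.** The plan gives no figure to reproduce; the check compares the windows and counts days.

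**End of the on-treatment window.** Inputs: 28-day cycles, dosing every 2 weeks, up to 24 cycles (section 3.2.1). Take Cycle 1 Day 1 as day 1. Doses fall on days 1 + 14k for k = 0 to 47, which is 48 doses, the last on day 23 × 28 + 15 = 659. Let C be the day of the last cetuximab dose and N the day of the last nivolumab dose.

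- Current window end: C + 100.
- Window end on either drug: max(C, N) + 100.
- Difference: max(0, N − C).

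The documents give no frequency for nivolumab continuing alone, so the first two rows are an assumed range, with N = 659.

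| Last cetuximab | C | Current end | Either-drug end | Difference | Nivolumab doses after current end |
|---|---|---|---|---|---|
| C1D15 | 15 | 115 | 759 | 644 days | 39 |
| C12D15 | 323 | 423 | 759 | 336 days | 17 |
| C24D15 (both stop together) | 659 | 759 | 759 | 0 | 0 |

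Dose counts: the first dose after day 115 is k = 9 (day 127), leaving 48 − 9 = 39. The first after day 423 is k = 31 (day 435), leaving 48 − 31 = 17.

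If N − C is 100 days or less, every nivolumab dose still lies inside the window and only the period after the last dose is shortened. Events during dosing fall outside only when nivolumab continues for more than 100 days after the last cetuximab dose. If nivolumab stops first, the two definitions agree.

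**Start of the window.** It opens at the first cetuximab dose, the lead-in on Day -14. Required reporting starts at Cycle 1 Day 1. The first 14 days of the window (Day -14 to Day -1) therefore have no required adverse event data.

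**30 against 100 days.** Footnote i has toxicities followed to resolution if they arise up to 30 days after therapy. Section 7.2.5 requires at least 100 days of follow-up. It also has all events followed until resolved or sufficiently characterised, unless the principal investigator decides not to pursue them. The two differ over 100 − 30 = 70 days for a patient who starts no new therapy.

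**Can the first 3-monthly visit cover day 100?** End of Treatment is 30 ± 3 days after the final dose, and the next visit is 3 months later (90 or 91 days) ± 14 days.

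- Earliest: 27 + 90 − 14 = day 103.
- Nominal: 30 + 90 = day 120, or 30 + 91 = day 121.
- Latest: 33 + 91 + 14 = day 138.

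On this schedule the visit falls after day 100 throughout, so it can capture the whole period, provided toxicity is asked about. Footnote a allows an earlier End of Treatment visit when new therapy is about to start, but the 100-day follow-up is waived once it has.

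**Is the blank cell real?** The table was machine-read, so caution is due. However, the history and physical, liver panel, TSH and survival rows all carry a mark in the same column, so the column survived and the blank is probably genuine.

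**The case against.** The strongest reply is that no stated analysis uses the on-treatment label. Section 10.1.2 plans a toxicity table by major category and highest grade, with no on-treatment filter, and section 7.1 lists overall incidence. A reader might infer that late nivolumab events would drop out of the safety table and the toxicity of the combination would be understated. The documents do not support that. Nor do they support the idea that such events would be missed: collection, follow-up and reporting in section 7.2.5 are not tied to cetuximab, and related events after 100 days stay reportable. This part of the reply stands.

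The premise of nivolumab alone is also narrow. Section 3.3.4 opens by removing patients from study for its listed events, which include grade 3 or 4 infusion reaction and grade 4 hypertension. Section 4.4.3 withdraws patients with grade 3 or 4 cetuximab reactions from treatment, and section 5.1.5.1 removes those with anaphylaxis of any grade. No passage describes nivolumab continuing alone. What remains is mainly unresolved rash and a second hypersensitivity reaction; neither is listed by name in section 3.3.4, and the text on both is silent about nivolumab.

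The rows with long gaps are extreme. Section 1.1.4 cites a median survival of 7.5 months on nivolumab, about 7.5 × 30.4 = 228 days, against dosing assumed to reach day 659. They illustrate the rule and do not estimate bias.

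Finally, a reader might take footnote i to end collection at 30 days and so discard 70 of the 100 days. It does not say so. It governs which toxicities are followed to resolution, and footnote b sends the first follow-up visit to section 7.2.5. The mismatch remains, as a risk that sites solicit too little.

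**Conclusion.** The point holds as two inconsistencies in the safety definitions.

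First, the on-treatment definition names one drug of two. It misclassifies events only if nivolumab is given after the last cetuximab dose, and then by exactly the gap between the two last doses: nil if both stop together, and 336 or 644 days in the assumed cases above. The documents neither clearly permit nor exclude this situation and give no frequency for it, so no expected size can be stated. The consequence is a wrong label on events that are still collected and reported.

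Second, footnote i and the unmarked toxicity cell do not match the 100-day follow-up. This could reduce solicitation in days 31 to 100 for events of either drug. It rests on the cell being truly blank and on sites following the calendar over section 7.2.5.

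Both deserve correction because section 7.2.5 holds the only on-treatment definition in the supplied text, and section 10.1.2 does not say whether the toxicity table will use it.

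**What to change.** 1. In section 7.2.5, end the on-treatment window 100 days after the last dose of either study drug, whichever is later. This works whether or not the drugs can stop at different times.
2. Align the start of the window with adverse event collection: open it at the first combination dose, or require lead-in events to be collected.
3. Reconcile calendar footnote i with section 7.2.5 so that one follow-up rule applies.
4. Mark toxicity assessment at the first 3-monthly visit, as footnote b and section 7.2.5 already imply.
5. Reconcile sections 3.3.4, 4.4, 4.4.2, 4.4.3, 4.5 and 5.1.5 on whether nivolumab may continue after cetuximab is permanently stopped. Which rule applies is for the sponsor to decide.

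The cost is wording. The first follow-up visit is already planned in clinic, where possible, for adverse event review. The downside is that slightly more events would count as on treatment.

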7.2.6. Responsibilities for SAE Reporting

Study Number: MCC 19178

The clinical management system being used for this study is The Online Collaborative Research Environment (OnCore). OnCore will be used to record all study related information for all registered subjects, including AEs and SAEs as defined in section 7.2.5. All serious adverse events (SAE) must be reported to Lilly Global Patient Safety via fax within 24 hours with a causality assessment, at [contact] or [contact]. In addition, all serious adverse events (SAE) must be reported to Brystol Myers Squibb within 24 hours with a causality assessment, either via fax to [contact] or via email to [contact].

8. BIOMARKER(S) AND CORRELATIVE STUDIES

Patients from the parent study will be eligible for participation on an optional basis in a tissue biomarker study and the mandatory blood collection for biomarker correlative study.

8.1. CORRELATIVE WITH TISSUE

Tissue/Specimen Submission

Tumor tissue samples will be collected at pre- and post-treatment (collected between day 8 and 15 of cycle 1 and before cetuximab and nivolumab treatment at Cycle 1 Day 15) and at the End of Treatment visit. The tumor tissue samples will be submitted to the [name]'s laboratory for banking and translational research.

Pre-treatment formalin-fixed paraffin-embedded (FFPE) tumor samples (MANDATORY)

An FFPE tumor block or sufficient slides (see Lab Manual for further details) should be submitted with the submission form. A Pathology Report and one hematoxylin and eosin-stained slide documenting that the submitted block or slides contain tumor should also be submitted with the tissue. The report and hematoxylin and eosin-stained slide must include

the protocol number and patient's case number. The patient's name and/or other identifying information should be removed from the report. The surgical pathology numbers and information must NOT be removed from the report. If the subject has multiple archival samples available, samples from various settings may be requested.

IND#: Exempt

Pre- and post-treatment tumor biopsy (collected between day 8 and 15 of cycle 1 and before cetuximab and nivolumab treatment at Cycle 1 Day 15) and at the End of Treatment visit for research purposed only (OPTIONAL)

The pre- and post-treatment tumor biopsy can be obtained from the primary tumor or lymph node metastasis as a punch biopsy or a core needle biopsy: one punch or core in formalin and the second punch or core in liquid nitrogen (or dry ice/ethanol slurry). Serial biopsies should be performed from the same site, if feasible, but can otherwise be collected from other sites of disease. The biopsy sample should be prepared (1) as a formalin-fixed paraffinembedded tumor block and shipped to [name]'s laboratory in ambient temperature, and 2) as a flash frozen sample in liquid nitrogen (or dry ice/ethanol slurry) and shipped to [name]'s laboratory on dry ice. The frozen specimens can be stored at -80°C (-70°C to -90°C) until ready to ship. If a -80°C freezer is not available, samples can be stored short term in a -20°C freezer (non-frost-free refrigerator preferred) for up to 7 calendar days (please ship on Monday-Wednesday only).

8.2. CORRELATIVE WITH BLOOD

Study Number: MCC 19178

Blood samples from participating sites external to Moffitt must be submitted with the submission form documenting the date of collection of the sample; the protocol number, the patient's case number, time point of study, and method of storage (for example, stored at -80°C). The frozen specimens can be stored at -80°C (-70°C to -90°C) until ready to ship. If a -80°C freezer is not available, samples can be stored short term in a -20°C freezer (non-frost-free refrigerator preferred) for up to 7 calendar days (please ship on Monday-Wednesday only).

Please refer to the laboratory manual for processing and shipment instructions.

Specimen collection summary for correlative studies (Samples can be batched and sent in one shipment)

Specimens for Correlative Studies			
Specimens taken from patient:	Collected when:	Submitted as:	Shipped:
A paraffin-embedded tissue of archival tissue taken before initiation of treatment	Pre-treatment	Paraffin-embedded tissue block, or unstained slides (see Lab Manual)	Block shipped ambient
Fresh frozen tissue of the primary or metastatic tumor taken before initiation of treatment (for research purposes only: OPTIONAL)	Pre-treatment	Frozen tumor in a 2 mL cryovial	Tumor sent frozen on dry ice via overnight carrier
A paraffin-embedded tissue of the primary or metastatic tumor (for	Post-treatment taken: 1) between day 8 and 15 of Cycle 1 and before	Paraffin-embedded tissue block	Block shipped ambient

[figure not shown]
research purposes only: OPTIONAL)	cetuximab and nivolumab treatment on Cycle 1 Day 15, 2) at the End of Treatment visit		
Fresh frozen tissue of the primary or metastatic tumor (for research purposes only: OPTIONAL)	Post-treatment taken; 1) between day 8 and 15 of Cycle 1 and before cetuximab and nivolumab treatment on Cycle 1 Day 15, 2) at the End of Treatment visit	Frozen tumor in a 2 mL cryovial	Tumor sent frozen on dry ice via overnight carrier
PLASMA: 10 mL of anticoagulated whole blood in EDTA tube (purple/ lavender top).	Pre-treatment and post-treatment taken: 1) between day 8 and 15 of Cycle 1 and before cetuximab and nivolumab treatment on Cycle 1 Day 15, 2) after 3 cycles of study drugs or 3 months from starting the treatment if off the study drugs, 3) at the End of Treatment visit 4) at the end of 2-year follow-up	Refer to Lab Manual for processing, storage, and shipping to Moffitt.	Plasma sent frozen on dry ice via overnight carrier
PBMC: 10 mL of anticoagulated whole blood in EDTA tube (purple/ lavender top).	Pre-treatment and post-treatment taken: 1) between day 8 and 15 of Cycle 1 and before cetuximab and nivolumab treatment on Cycle 1 Day 15, 2) after 3 cycles of study drugs or 3 months from starting the treatment if off the study drugs, 3) at the End of Treatment visit, 4) at the end of 2-year follow-up	Refer to Lab Manual for processing, storage, and shipping to Moffitt.	Non-Moffitt site: PBMC sent frozen on dry ice via overnight carrier

Submit materials for translational research as detailed in the lab manual.

Page 40 of 64

